1.2 SCHEMA

1.3 SCHEDULE OF ACTIVITIES (SOA)

Procedures	Pre-Index Visit	Index Visit – first study-eligible visit	18 months follow-up
Randomization of clinics to intervention or control	X		
Wizard runs in the background at the patient's primary care encounters. An encounter-based limited data set is collected and stored in a data repository (intervention & control).	X	X	X
Eligible patient is assigned a study identification (ID) for longitudinal follow up identification (intervention & control).		X	
Best Practice Advisory (BPA) occurs for rooming staff prompting CDS use for the eligible patient (intervention clinics)		X	
The eligible patient is exposed to CKD-CDS at a primary care encounter (intervention clinics)		X	
Shared decision making and action based on CKD-CDS recommendations (intervention clinics)		X	
Best Practice Advisory (BPA) occurs for rooming staff prompting CDS use for the eligible patient who previously received a BPA			X
The eligible patient who previously received a BPA is exposed to CKD-CDS at subsequent primary care encounter(s) (intervention clinics)			X
Shared decision making and action based on CKD-CDS recommendations (intervention clinics)			X
Safety monitoring per Data Safety Monitoring plan (intervention & control)		X	X

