9.2 SAMPLE SIZE DETERMINATION

We conducted an a priori power analysis for each of the 5 outcome measures to estimate the minimum detectable difference in each given assumptions about analytic sample size, proportions of patients meeting outcome criteria, and intra-class correlations, all estimated from 2015-2016 HPMG pilot data of patients meeting categories for stage 3-4 CKD. The correlated sample of CKD patients within clinics was reduced to an equivalently sized independent patient sample by dividing the anticipated sample size by the design effect introduced by clustering within clinics [Neff pt = N / [1 + (nclus-1)ICCclin]]. For the BP control outcome, the correlated BP sample size (M=Neff pt * m outcomes per patient) was adjusted to account for clustering within patients [Neff obs = M / [1+ (mclus-1)ICCpt]]. Based on the effective sample sizes, we estimated the minimum proportion of CKD-CDS relative to UC patients meeting criteria for each outcome at 12 m that would be powered to reach statistical significance (power=.80, α 2=.05).

Table 2 summarizes for each outcome the sample size, mean and intra-class correlation calculated from HPMG pilot data; the data-informed assumptions used in the power analyses; and the minimum

detectable and clinically meaningful differences among CKD-CDS versus UC patients. Power analysis assumptions were either consistent with or more conservative than pilot estimates. For each outcome, the minimum statistically detectable difference is smaller than the clinically meaningful difference, even under these relatively conservative assumptions. For example, the H1 analysis is powered to detect increases in diagnosis rates of 5.8%-11.1% among CKD-CDS relative to UC patients, a difference that is notably smaller than the 20% increase that would represent significant clinical improvement and should be attainable with the CKD-CDS intervention.

Table 2. Summary of descriptive statistics calculated from HPMG pilot data, key power analysis assumptions, and minimum detectable difference in 12-month post-index outcomes among CKD-CDS relative to UC patients for Hypothesis 1 to 5 outcomes.							
	CKD Dx	ACEI / ARB	BP < 140/90	BP < 130/80	A1c <8	A1c <7	Neph referral
HPMG pilot data estimates							
N ^a	10175	9012	8975	8975	3191	3191	1161
M (%)	52.9	54.6	70.4	43.3	79.7	48.7	37.8
ICC _{clin}	.027	.003	.004	.004	0	.003	0.063
ICC _{pt}			.28	.26			
Power assumptions							
M (%)	50-60	50-60	70-80	40-50	75-85	40-50	30-40

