ICC _{clin}	.01-.05	.001-.01	.001-.01	.001-.01	.001-.01	.001-.01	.05-.10
ICC _{pt}			.25-.35	.25-.35			
Minimum detectable and clinically meaningful differences (%)							
detectable	5.8-11.1	3.4-5.7	3.2-7.1	4.3-8.4	3.5-5.9	5.2-7.0	13.5-17.9
meaningful	20	10	10	10	10	10	20

^aestimated from number eligible in 17 HPMG clinics, prorated to 30 clinics assuming 13 similarly sized PN clinics

Pilot data from 2015-2016 primary care visits at 17 HPMG clinics found N=5766 adult patients aged 18-80 who had laboratory evidence of stage 3-4 CKD in 2015 and at least 1 post-index follow-up visit (median=5) before the end of 2016. PN primary clinics are similar in size and patient characteristics, suggesting a prorated N≈10,175 eligible CKD patients, including data from 13 additional PN clinics. We anticipate about 6% disenrollment from the medical group per year and about 2% per year to die. Very few patients switch from one clinic to another within HPMG or PN, and our algorithms accurately match over 95% of patients to a single PCP. In sum, we expect that data from a robust sample of patients with CKD will be available for testing Hypotheses 1-5. We will retrospectively retrieve the minimal necessary set of clinical information for conducting primary analyses as a limited dataset from the data repository that supports CKD-CDS operations.

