9.4.2 ANALYSIS OF THE PRIMARY EFFICACY ENDPOINT(S)

9.4.2.1. Analysis plan. All hypotheses will be tested using random coefficients models in which each binary post-index outcome (e.g., recognition in 18m) will be predicted via a link function from a fixed clinic-randomized treatment group predictor, Y_{10} ; fixed clinic predictors for characteristics balanced at randomization, Y_{*0} ; a fixed pre-index outcome status where appropriate, Y_{01} ; and a random clinic intercept, V_j , such as:

$$\text{logit}(BP<130/80 18m_{ji}) = Y_{00} + Y_{10}\text{CKD-CDS}_j + Y_{*0}\text{balancing}_j + Y_{01}\text{SBP index}_i + [V_j].$$

Parameter Y_{10} is expected to be positive and statistically significant, indicating that patients in clinics randomly assigned to receive the CKD-CDS intervention are more likely to meet CKD recognition (H1), ACEI / ARB use (H2), BP control (H3), A1C control (H4) and nephrology referral (H5) thresholds in the 18 months post-index than patients in UC clinics, accounting for random variation across clinics and their own pre-index status on these outcomes.

The difference in predicted likelihoods of meeting each of the 5 outcomes through 18 months post-index will be estimated via planned contrasts and reported for ease of interpretation.

Secondary outcomes may be calculated using different thresholds (e.g., A1c<8) or treated as continuous variables (e.g., SBP in mm Hg) with adaptations made to the analysis models as necessary (e.g., identity link). Secondary analyses may include assessing (a) rates of treatment intensification among patients not at their BP or glucose goals, (b) variation in CKD treatment patterns across PCPs, (c) treatment effect heterogeneity, (d) intervention costs, (e) rate of occurrence and time to major CV events, and (e) rate of occurrence and time to hospital admissions or emergency department visits by eligible study subjects by treatment arm. We may also assess the impact of the CKD-CDS on NSAID use and medication adherence and treatment heterogeneity across demographic and racial groups.

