9.4.2.2. Key Covariates. A key covariate in the H1-H5 hypothesis tests will be a binary indicator to denote whether the clinic in which the patient is seen was randomly assigned to the CKD-CDS intervention or the UC arm of the study. A second, pertinent to H3, quantifies the amount of time elapsed between the index visit and each measured BP. This covariate will be coded as (days since index/365) so that it quantifies the predicted annual change in BP control. Similarly, should the time elapsed between index and the last observed A1C differ by treatment group, log (time elapsed) may be included as an offset in the H4 analysis. Index CKD stage may be an important modifier of the CKD-CDS intervention. Stage 3-4 CKD will be defined based on the eGFR of 15-59 cc/min/1.73m² on the most recent eGFR test before the date of an index visit (stage 3a = 45-59, stage 3b = 30-44, stage 4 = 15-29), plus 1 or more antecedent eGFR values <60 cc/min/1.73m². Several other measures merit consideration as either secondary outcomes or as mediators or moderators of the primary analyses. These include (a) number of PCP patient encounters, (b) patient characteristics, including demographics and pre-intervention clinical

values and comorbidities (ICD-10 diagnosis codes and problem lists), and (c) PCP variation in baseline measures of CKD care.

9.4.2.3. Missing data. Data elements required for calculating the primary outcomes are extracted from EHR production tables. The absence of documentation of a care process, vital sign, or medication should not be interpreted as a missing value but rather as indicative of a care process or test not having been performed or medication not prescribed within the health system. Truly missing observations (eg, systolic BP measured, value not available) will be extremely rare, undetectable and assumed to be missing at random (MAR). The estimation techniques used in random coefficient models readily accommodate structural variation across observations in the amount of data present (eg, patients per clinic) and lead to unbiased parameter estimates and accurate standard errors when data are MAR.

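### Section 9.4.2.1 could gain precision for H1 and H5 cheaply: list the balancing factors and, unless already among them, add the clinic's own pre-trial outcome rate

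*Combined protocol and SAP*

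**What the plan says.** Section 9.4.2.1 gives one logistic model for all five hypotheses. Its terms are treatment arm, "fixed clinic predictors for characteristics balanced at randomization", "a fixed pre-index outcome status where appropriate" (subscripted at patient level in the worked example), and a random clinic intercept. Section 4.1 says that constrained randomisation balanced the arms on important factors but does not name them. No other section does.

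Section 9.4.2.2 comes nearest to a baseline level of care with "PCP variation in baseline measures of CKD care". That is at provider level, and it is listed only as a possible secondary outcome, mediator or moderator.

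Section 9.3 restricts each hypothesis to patients who have the matching care gap at index. Section 9.2 sizes each outcome with "Neff pt = N / [1 + (nclus-1)ICCclin" for differences "powered to reach statistical significance (power=.80, α 2=.05". In Table 2 the pilot clinic ICC is .027 for H1 and .063 for H5, and .004 or less for the other outcomes.

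**The concern.** In a clinic-randomised trial with a sizeable ICC, precision depends mainly on how far clinics differ, not on how many patients each contributes. A covariate helps to the extent that it explains those clinic differences.

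H3 and H4 can use the patient's index BP or A1c. H1 and H5 have no comparable term. Nobody enters the H1 set with CKD established in the record by the gap definition, and nobody enters the H5 set with a nephrology visit completed in the prior year. Stable clinic habits in coding or referral therefore stay largely in the random intercept.

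The clinic's earlier rate of the same outcome is the natural predictor of those habits. If it is not among the unnamed balancing factors, the two outcomes most affected by clustering are analysed less precisely than existing data allow. A chance difference in starting levels between about 16 clinics per arm would then also go unadjusted.

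**Working it through.** **Inputs.** From Section 9.2 and Table 2: N = 10,175 for H1 ("suggesting a prorated N≈10,175 eligible CKD patients") and 1,161 for H5; pilot ICCs .027 and .063; assumed control rates 50-60% and 30-40%; 30 clinics. From Section 5.5: 32 clinics enrolled. Not in the documents: r, the correlation between a clinic's observed pre-trial rate and its trial-period rate. I take .3, .5 and .7.

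**Reproducing Table 2.** I use 30 equal clinics, 1:1 allocation, DE = 1 + (n - 1) x ICC, and a two-sided .05 test of two proportions at 80% power.
- H1: 5.8 points (ICC .01, 50%) and 11.1 (ICC .05, 60%). Stated: 5.8-11.1.
- H5: 13.4 points (ICC .05, 30%) and 17.9 (ICC .10, 40%). Stated: 13.5-17.9.

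**Share of the contrast variance due to clinics**, n x ICC / DE, at the pilot ICCs:
- H1: n = 10,175/30 = 339.2; DE = 1 + 338.2 x .027 = 10.13; share = 339.2 x .027 / 10.13 = .90.
- H5: n = 1,161/30 = 38.7; DE = 1 + 37.7 x .063 = 3.38; share = 38.7 x .063 / 3.38 = .72.

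The DE is 1.9 for ACEI/ARB, 2.2 for BP at clinic level and 1.0-1.3 for A1c, so H1 and H5 are where a clinic covariate has most to offer.

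**Effect of the covariate**, with 32 clinics: DE = 1 + (n - 1) x ICC x (1 - r²), and detectable difference = 2.80 x sqrt(4pq x DE / N). Control rates are 50% (H1) and 35% (H5).
- H1 without it: DE = 1 + 317.0 x .027 = 9.56; 2.80 x sqrt(1 x 9.56 / 10,175) = 8.6 points.
- H5 without it: DE = 1 + 35.3 x .063 = 3.22; 2.80 x sqrt(0.91 x 3.22 / 1,161) = 14.1 points.

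Table 2 counts all eligible patients, but the analysis sets hold only gap patients. Table 1 suggests gap shares of 100 - 49.2 = 50.8% (H1) and 100 - 45.6 = 54.4% (H5; a two-year look-back, against one year in Section 5.1). That gives 10,175 x .508 = 5,169 and 1,161 x .544 = 632 patients. The ICC among gap patients is not given, so the pilot ICC is carried over.

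| Set | No covariate | r = .3 | r = .5 | r = .7 |
|---|---|---|---|---|
| H1, N 10,175 | 8.6 | 8.2 (-4%) | 7.6 (-12%) | 6.4 (-25%) |
| H5, N 1,161 | 14.1 | 13.6 (-3%) | 12.8 (-9%) | 11.5 (-19%) |
| H1, gap-only 5,169 | 9.0 | 8.7 (-4%) | 8.0 (-11%) | 7.0 (-22%) |
| H5, gap-only 632 | 15.7 | 15.3 (-3%) | 14.6 (-7%) | 13.4 (-14%) |

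**How large r can be.** Sampling noise in the baseline rate limits it. Reliability is n x ICC / DE. For H5 gap-only, n = 632/32 = 19.8 and reliability = 19.8 x .063 / 2.18 = .57, so observed r cannot exceed sqrt(.57) = .75. Reaching .7 would need a true clinic-level correlation of about .7/.755 = .93. The 14% figure is therefore close to a ceiling.

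**The case against.** Four objections carry weight.

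1. **The adjustment may already exist.** A reader might infer that the model omits clinic baseline performance. The documents do not show that. Every balancing factor enters the model, and because the factors are unnamed, a baseline CKD-care rate could be one of them. This stands, and it is why the first request is to list them.

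2. **Pre-index status is not strictly constant.** The H1 gap (Section 5.1) allows a CKD code at one outpatient encounter, while the H1 outcome (Section 9.1) needs only one code. The H5 gap concerns completed visits in the prior year, while the outcome also counts referrals, so an older visit or an uncompleted referral can differ between patients. This stands: the term is nearly constant and can absorb little, but not nothing.

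3. **There is no power shortfall.** A reader might infer that H1 or H5 is underpowered or the model invalid. Neither follows. The largest stated detectable differences, 11.1 and 17.9 points, are below the 20 points called meaningful. At 20 points, worst-case power is above 99% for H1 and about 88% for H5.

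4. **r is assumed and could be low.** Section 4.2 describes clinic closures, provider moves and a shift to telehealth from March 2020, during follow-up. Any of these could weaken the link between pre-2019 and trial-period rates. This stands. At r = .3 the gain is only 3-4%.

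**Conclusion.** This is a worthwhile, inexpensive improvement, not a correction of a faulty analysis. What the documents support is that no clinic-level pre-trial outcome rate is named, the balancing factors are not listed, and the patient-level term can do little for H1 and H5, where clinics account for about 90% and 72% of the contrast variance.

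The likely reduction in detectable difference is 3-4% at r = .3, 7-12% at r = .5 and 14-25% at r = .7. These figures assume equal clinic sizes, a normal approximation, the pilot ICCs, and that the rate is not already a balancing factor. Because power against 20 points is already adequate, the return is narrower intervals and less exposure to chance imbalance between about 16 clinics per arm.

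**What to change.** In Section 9.4.2.1:

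- List the characteristics balanced at randomisation.
- Unless it is already among them, pre-specify for H1 and H5 one clinic-level covariate: the index clinic's rate of the same outcome among gap patients, by the same definitions, in a fixed EHR window closing before go-live in April 2019. Treatment cannot then have affected it.
- State the window. A full 18-month outcome needs index dates before about October 2017. If the data do not reach that far back for all 32 clinics, name a shorter outcome window and use it in every clinic.
- Settle this before any outcome comparison by arm.

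The cost is SAP wording, one EHR pull and one clinic-level degree of freedom. With 32 clinics and no other clinic covariates, the t critical value moves from 2.042 (30 df) to 2.045 (29 df). The balancing factors already use some degrees of freedom, but the further loss is still small.

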4.2 SCIENTIFIC RATIONALE FOR STUDY DESIGN

The CKD-CDS intervention provides timely, data driven information to providers at primary care visits with patients who have CKD and a deficit in CKD care. Because it is common for patients to see more than one clinician over time, particularly in the same clinic, there is significant risk of contamination if the intervention were to be randomized at the patient or provider level. However, patients tend to receive most of their care over time at a single clinic, and clinicians tend to practice at a single clinic. For this reason, contamination risk across clinics is relatively low. The cluster-randomized trial design

randomizes primary care clinics to usual care or CKD clinical decision support to minimize risk of contamination.

Clinics were randomly allocated 1:1 to intervention or usual care based on the results of a computer-generated algorithm. From the time the CKD-CDS tool was implemented in April, 2019, through March, 2020, the CKD-CDS interface was programmed to display at eligible visits in clinics randomized to the CKD-CDS intervention group. As a result, intervention-eligible patients were exposed to the intended treatment at visits that took place in a clinic assigned to the same treatment group as their index visit clinic.

The care systems responded to the COVID-19 pandemic in March, 2020, by closing or realigning many of the randomized clinics, making significant changes to the clinics at which providers practiced and shifting from in-person to telehealth visits. The clinic closures and changes in provider locations disrupted what had been reliable correspondence between patients and clinic locations; and hence, made exposure to the intended treatment group unreliable. The shift in visit modality made it very difficult to access the CKD-CDS interface (i.e., the intervention) during visits. Index visits were suspended as of March, 2020, and the CKD-CDS interface was turned off between March and August, 2020, to prevent unreliable intervention delivery and technological challenges.

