4.4 END OF STUDY DEFINITION

The end date for the study is defined as the date that corresponds to 18 months after the index visit of the last person enrolled at a study clinic during the 11 month patient accrual period. Note that the accrual period was shortened from 12 to 11 months due to the onset of the Covid-19 pandemic in March 2020. The pandemic also caused disruptions in care delivery and decreased volume of primary care encounters in mid-2020 which interrupted intervention delivery during this period. We extended the follow-up period from 12 months to 18 months to increase the number of patients with primary care encounters and follow-up measures needed to assess intervention impact.

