Glucose care gap	4.1) diagnosed diabetes; and 4.2) A1c above goal	4.1) ICD-10 codes E10, E11 at 1 inpatient or 2 outpatient encounters, or on the problem list, in the previous 2 years; and 4.2) most recent A1c>=7 on or before index date
Nephrology care gap	5.1) Stage 3b or 4 CKD; and	5.1a) most recent eGFR15-<30 cc/min/1.72m ² , or

	5.2) nephrology referral needed	5.1b) eGFR30-<45 cc/min/1.72m ² and UMACR >=30 mg/g; and 5.2) no completed nephrology visit in prior year
--	---------------------------------	---

The index visit is defined as the first visit at any randomized clinic during the accrual period at which the patient met these CKD-CDS intervention eligibility criteria and none of the exclusion criteria. The patient accrual period (for index visits) was 11 months, followed by a 18-month observation period, so that patients will have 18 to 29 months of post-index follow up (estimated median, 24 months).

Each patient was assigned to the clinic where their index visit took place and by extension to the randomized treatment group of that clinic. Patients with index visits at clinics randomized to the CKD-CDS intervention (or usual care) group were considered CKD-CDS intervention (or usual care) patients. A patient could have post-index visits, that may or may not be intervention eligible, at clinics randomized to the other treatment group. Following intent to treat principles, the patient's treatment group assignment will not change as a result of the clinic treatment group assignment or patient intervention eligibility at the post-index visits. Additionally, the index visit marks the beginning of each patient's 18-month observation period.

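### The five primary models have no index-date term, although the share of the 18-month outcome window after March 2020 runs from about 39% to nearly 100%; adding quarter of index visit is a cheap safeguard, not a correction of bias

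*Combined protocol and SAP*

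**What the plan says.** **Model.** Section 9.4.2.1 lists the terms used for every hypothesis: arm, clinic characteristics balanced at randomisation, "a fixed pre-index outcome status where appropriate", and a random clinic intercept. Section 9.4.2.2 adds time from index to each BP for H3 and an optional log elapsed-time offset for H4. H1, H2 and H5 have no time term. Section 9.4.5 accepts that adjustment for patient covariates may be needed but does not name index date. Neither do the moderator lists in Sections 9.4.2.2 and 9.4.7.

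**Calendar.** Section 5.1 states: "The patient accrual period (for index visits) was 11 months, followed by a 18-month observation period", and that "the index visit marks the beginning of each patient's 18-month observation period". Section 4.2 describes clinic-based display of the tool: "From the time the CKD-CDS tool was implemented in April, 2019, through March, 2020". It then reports: "The care systems responded to the COVID-19 pandemic in March, 2020, by closing or realigning many of the randomized clinics", with providers relocated and visits moved to telehealth. It adds: "Index visits were suspended as of March, 2020, and the CKD-CDS interface was turned off between March and August, 2020". Delivery resumed in August 2020, with the assigned arm following the patient to any clinic or visit type. Section 4.4 refers to "decreased volume of primary care encounters in mid-2020 which interrupted intervention delivery during this period" and lengthens follow-up from 12 to 18 months in response.

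**Undocumented care.** Section 9.4.2.3 treats care that is not documented as care not given, rather than as missing data.

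**The concern.** All five outcomes are read from routine care, and the protocol itself says that routine care changed abruptly in March 2020. Two patients with the same 18-month window can have very different mixes of care before and after that date, depending only on index month. Fewer contacts can mean fewer recorded diagnoses, orders, referrals and measurements, and Section 9.4.2.3 counts these as outcome not met. Index month is therefore a plausible predictor of every outcome, it is known for every patient, and it is not in the model. The elapsed-time terms do not replace it: a BP taken 12 months after index falls in April 2020 for one patient and in February 2021 for another.

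Two things are at stake. With only 32 clinics, the arms may differ by chance in accrual timing, and the plan names no adjustment for that. A single pooled effect also averages over two ways of delivering the tool (by clinic, then by patient), and no planned analysis looks at them separately.

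**Working it through.** 1. **The plan's own calendar figure.** Section 5.1 gives 18 to 29 months of post-index follow-up, median about 24. Check: 18 + 11 = 29. With even accrual the median is 18 + 11/2 = 23.5. The figure reproduces.

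2. **Share of the window after the disruption, and tool-available time.** The documents give months, not days. Assumptions: disruption from 1 March 2020; tool off from 1 March to 1 August 2020 (5 months).
   - Months before March 2020 = b.
   - Share after = (18 − b)/18.
   - Tool-on months after the restart = 18 − b − 5.

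| Index date | Window ends | b | Share after | Tool-on months, before + after |
|---|---|---|---|---|
| 1 Apr 2019 | 1 Oct 2020 | 11 | 7/18 = 39% | 11 + 2 = 13 |
| 1 Jul 2019 | 1 Jan 2021 | 8 | 10/18 = 56% | 8 + 5 = 13 |
| 1 Oct 2019 | 1 Apr 2021 | 5 | 13/18 = 72% | 5 + 8 = 13 |
| 1 Jan 2020 | 1 Jul 2021 | 2 | 16/18 = 89% | 2 + 11 = 13 |
| 1 Feb 2020 | 1 Aug 2021 | 1 | 17/18 = 94% | 1 + 12 = 13 |
| 1 Mar 2020 | 1 Sep 2021 | 0 | 18/18 = 100% | 0 + 13 = 13 |

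3. **Sensitivity to the assumed days.** For a 1 April 2019 index visit, the share is 36% if the disruption starts on 15 March and 6/18 = 33% if it starts on 1 April. For a 30 April 2019 index visit with a 1 March start it is 44%. At the other end, an index visit on 29 February 2020 gives 99.8%. Index visits were suspended as of March, so few patients can reach 100%. With 11 even index months the mean share is (7 + 5)/18 = 67%. Counting March as a full twelfth month gives (7 + 5.5)/18 = 69%. If the tool was off for 6 months, as Section 8.2 suggests, tool-on time is 12 months in place of 13 and still does not vary with index month.

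4. **Size of a chance imbalance (assumptions only).** Shift in the contrast = change in outcome rate per index month × arm difference in mean index month. The documents give neither factor. With 0.5 to 2 points per month, in either direction, and 0.25 to 1 month, the shift is 0.5 × 0.25 = 0.1 to 2 × 1 = 2 points. The upper slope means 2 × 11 = 22 points across accrual. If clinic mean index dates had an SD of 0.1 of the accrual period (0.1 × 11 = 1.1 months), then with 16 equal clinics per arm and simple randomisation the arm difference would have an SD of 1.1 × √(2/16) = 0.39 month. A one-month difference would be about 2.6 SDs. At 0.39 month the shift is 0.2 to 0.8 points.

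5. **Illustrative simulation with and without the term.**
   - Assumptions: 32 clinics, 150 patients each, base rate 50%, the pilot ICC of .027 for H1, the same accrual process in both arms, and era effects from none to an odds ratio of 0.16 for last versus first index month. The test was a t-test on clinic means, not the planned logistic mixed model.
   - Without the term, type I error was between about 4% and 6%, and the mean difference under the null was within about 0.2 points of zero.
   - The estimated treatment difference was the same with and without the term (for example 9.2 and 9.2 points).
   - Adding the term changed power by about 2 points or less when clinics shared one index-date distribution. The largest gain, about 8 points (roughly 80% to 88%), needed the most extreme era effect together with clinic shifts of SD 0.1 of accrual.
   - Omission attenuated the conditional log odds ratio by about 0.5% to 4.5%.

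**The case against.** The strongest case is that nothing here is an error. Accrual was concurrent, clinics were randomised 1:1, and Section 5.1 says that nobody could influence when a visit became the index visit. Era is therefore balanced between arms in expectation. A chance imbalance is ordinary sampling error, and much of its clinic-level part is absorbed by the random intercept. The plan also responds in part: follow-up was lengthened, patient-covariate adjustment is allowed, and the number of primary care encounters is listed as a possible moderator or mediator. All of this stands, and it rules out three stronger readings that a reader might infer.

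- **A strong era effect has gone unadjusted.** The documents describe disruption but report no outcome rate by period. Even the direction is open. H3 and H4 use the most recent values, and windows opened in April 2019 close about October 2020, soon after the mid-2020 drop in visits. Windows opened in February 2020 close about August 2021. Later index could help on those two outcomes.
- **The treatment contrast is biased.** That would need arm and index date to be linked by design, as in a stepped-wedge trial. They are not.
- **Tool exposure falls from 11 months to none with later index.** That counts only the time before March 2020. Total availability is constant, as the table shows; only its split between clinic-based and patient-following delivery changes.

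What the objection does not answer is why a plausible baseline predictor, already held for every patient, is left to discretion. Section 9.4.5 leaves open which covariates are used and when, so a decision about pandemic adjustment could be taken after results are seen.

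**Conclusion.** The omission is confirmed, and it is a minor one. The range of about 39% to nearly 100% follows from the protocol's dates, with a low end of 33% to 44% depending on the assumed days. It shows that index period varies enough to be worth a term. It does not show that outcomes differ by index period, nor that the planned comparison is invalid. Under the assumptions above, a chance imbalance would move a contrast by roughly 0.1 to 2 points in either direction, with the upper end unlikely. The precision gain would usually be small. The case for change is that the term is prognostic on the protocol's own account of events, cannot be affected by the intervention, and costs almost nothing.

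**What to change.** Add quarter of index visit (April–June 2019, July–September 2019, October–December 2019, January–March 2020) as a fixed patient-level categorical covariate in all five primary models. Categories avoid assuming a direction or a straight line. State that the reported differences in predicted likelihood are averaged over the observed distribution of index quarter. Specify this before outcomes are examined by arm. If that point has passed, label it a sensitivity analysis.

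Report a treatment-by-index-period interaction (April–September 2019 versus October 2019–March 2020) as supportive only. Say in the plan that it cannot isolate delivery mode: the index visit is the first eligible visit in the accrual period, so frequent attenders tend to be indexed early and index month also tracks visit frequency.

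The cost is 3 patient-level degrees of freedom per model, none at clinic level, one additional table and no new data.
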